Disease evaluation by Response Evaluation Criteria in Solid Tumours (RECIST) v1.1 and immune RECIST (iRECIST) (solid tumours only)		X h			X i		X i	X i	X i	h. Scans within 4 weeks of screening will be accepted. i. Using standard of care scan schedule for the specified solid tumour. The first radiographic scan after receiving SUPLEXA will be performed at Week 6-12 weeks after the 1st SUPLEXA infusion and thereafter every 6-12 weeks depending on tumour type and as clinically indicated per investigator's discretion.

Study period	Screening		Treatment Period (Weekly dosing)		TREATMENT GAP	Treatment Extension Period	Follow Up after last dose		Notes	
			SUPLEXA Batch 1							
Study Treatment Week	-5	-5 to -1	First 3 infusions	Additional doses 		Doses 				
Visit Window (days)		±2		±2		60	-1 to +7	±5		
			Week 0 Day 1/ Baseline	1, 2			Every 8 weeks up to 48 weeks from last dose	EOS/ET	End of Study (EOS) will be conducted within 30d for all subjects who completed the study per protocol; Early termination (ET) visit will be conducted within 30d or subjects who withdraw from the study prematurely.	
Disease evaluation for haematologic malignancies only		X		X*		X*	X*	X	*As clinically indicated, may also be conducted every 4 weeks, starting 4 weeks after the 3 rd dose	
Complete blood count (CBC) with differential and blood chemistry	X		X j	X j, k	X j	X j	X	X	Refer to Table 5 for list of parameters to be evaluated j. Predose k. Repeat at baseline in local hospital lab for stat results, and central lab sample to be shipped	
Collect blood for pharmacodynamic immune assessments, including cytokines			X	X	X	X	X l		Refer to Section 8.4 for list of parameters to be evaluated l. collected where possible post dose	

Study period	Screening		Treatment Period (Weekly dosing)		TREATMENT GAP	Treatment Extension Period	Follow Up after last dose		Notes	
			SUPLEXA Batch 1							
Study Treatment Week	-5	-5 to -1	First 3 infusions	Additional doses 		Batch 2				
			Week 0 Day 1/ Baseline	1, 2		Doses 				
Visit Window (days)		±2		±2	±2	-1 to +7	60	-1 to +7	Every 8 weeks up to 48 weeks from last dose	EOS/ET
Serology		X m							Refer to Table 5 for list of parameters to be evaluated	

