#### 4.1.2.3 Disease Evaluation

For subjects in the solid tumours cohort, the on-treatment radiographic assessments of chest, abdomen, and pelvis will be performed per standard of care intervals throughout the course of the study.

The first radiographic scan after receiving SUPLEXA will be performed at Week 6-12 weeks after the 1st SUPLEXA infusion and thereafter every 6-12 weeks depending on tumour type and as clinically indicated per investigator's discretion.

These scans should be available for assessment by the Sponsor, if requested. The response evaluation will be assessed by the Investigator according to RECIST v1.1 and iRECIST until unequivocal radiographic disease progression, or until the subject starts a subsequent anticancer therapy (whichever comes first). The tumour assessment (imaging) for confirmation of response should be performed no less than 4 weeks after the criteria for response are first met. All radiographic scans will be collected and held for possible future retrospective evaluation by BICR.

For subjects in the haematological malignancies cohort, disease evaluation will be conducted every 4 weeks, as clinically indicated throughout the study.

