#### 4.1.3 Follow-up – All Subjects

All subjects will be followed up every 8 weeks for 48 weeks post last dose of study intervention; visits can be done remotely or in-clinic.

The end of study (EOS) or early termination (ET) visits must be done in person.

Beyond 48 weeks post last dose of study intervention, subjects will be contacted for survival status, disease status and initiation of subsequent anticancer therapies every 12 weeks up to a maximum of 24 months after the last dose of study intervention or earlier if the study is terminated by the Sponsor.

Subjects who permanently discontinue study intervention early will be encouraged to remain in the study (refer to Section 7.2). Subjects who begin new anti-cancer therapy after discontinuation of study intervention will be permanently withdrawn from the study.

Subjects who withdraw early from the study will be followed-up via phone or in person every 12 weeks at a minimum or sooner as required by the Investigator to determine OS and PFS.

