### 7.2 DISCONTINUATION OF STUDY INTERVENTION

In some instances, it may be necessary for a subject to permanently discontinue study intervention. Please also refer to stopping rules described in Section [7.1](#).

A subject must permanently discontinue study intervention if they meet one of the following individual stopping rules:

- Any Grade 4 life threatening events assessed as related to study intervention.
- $\geq$ Grade 3 immunological-related event assessed as related to study intervention (refer to Section [7.2.1](#))

A subject may also discontinue study intervention for reasons including but not limited to:

- Adverse event
- Lost to follow-up
- Non-compliance with study drug
- Physician decision
- Pregnancy (refer to Section [7.2.2](#))
- Progressive disease
- Protocol deviation
- Study terminated by Sponsor
- Withdrawal by subject
- Death

Permanent discontinuation of study intervention does not mean withdrawal from the study, and the subject will be encouraged to remain in the study, complete the ET visit and then continue to complete all study visits as per the SoA, including all follow-up visits.

For subjects who have discontinued study intervention due to reasons other than disease progression, tumour assessment will be continued at the protocol-specified schedule until documented disease progression or initiation of subsequent anticancer therapy or until 24 months after the last dose of study intervention.

The primary reason for discontinuation from study intervention should be documented on the appropriate eCRF.

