##### Exploratory

- DOR will be defined as the time from the first date of objective response (CR or PR) to the first documented date of disease progression or the date of death due to any cause, whichever occurs first. Only subjects with a CR or PR will be included.
- TTR will be defined as the time from the first dose of study intervention to the first date of objective response (CR or PR). Only subjects with a CR or PR will be included.
- CBR will be defined as the proportion of subjects with a CR or PR or SD at 6 months.
- PFS will be defined as the time from the first dose of study intervention to the first documented date of disease progression or the date of death due to any cause, whichever occurs first.
- OS will be defined as the time from the first dose of study intervention to the date of death due to any cause.
- Biomarker change from baseline with time as % and absolute.

Main analyses of the above response-related endpoints will be performed in the Efficacy Evaluable Population using Investigator-assessed response. Sensitivity analyses of the above response-related endpoints may be performed in the Response Evaluable Population using Investigator-assessed response. If response is also assessed by BICR, further sensitivity analyses of the above response-related endpoints may be performed using BICR-assessed response.

CBR will be analysed in a similar manner as the primary endpoint of ORR.

Time-to-event endpoints (DOR, TTR, PFS, TTP, and OS) will be summarized using Kaplan-Meier estimates. If estimable, median, 25th, and 75th percentiles and associated 95% CIs will be presented. A Kaplan-Meier curve will also be generated for each time-to-event endpoint. For time-to event endpoints, censoring rules will be applied as follows. DOR will be censored at the last tumour assessment date. PFS and TTP will be censored at the last tumour assessment date

for subjects with post-baseline assessment (s). OS will be censored at the last known date alive for subjects.

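### Three sections disagree on when tumour assessment ends; if scans stop 48 weeks after last dose, the stated censoring rule drives the late PFS and DOR curves towards zero

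*Combined protocol and SAP*

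**What the plan says.** Three places set the end of tumour assessment.

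- **Section 7.2:** a subject who came off treatment for any reason but progression keeps having scans, on the timetable set elsewhere in the protocol, "until documented disease progression or initiation of subsequent anticancer therapy or until 24 months after the last dose of study intervention". The rule covers only that subgroup. It does not say whether a subject who has used up the manufactured product belongs to it.
- **Schedule of Activities (Section 1.3):** the RECIST/iRECIST row is marked in the follow-up column headed "Every 8 weeks up to 48 weeks from last dose" and at the end-of-study/early-termination visit. There is no later scan column. The row's footnote begins "Using standard of care scan schedule for the specified solid tumour", gives 6- to 12-week intervals and names no end date.
- **Section 4.1.2.3:** response is assessed "until unequivocal radiographic disease progression" or until a subsequent anticancer therapy starts, whichever is earlier. There is no calendar limit.

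After 48 weeks, Section 4.1.3 says that "subjects will be contacted for survival status, disease status and initiation of subsequent anticancer therapies every 12 weeks", up to 24 months after last dose. The synopsis, the SoA footnote and Section 4.4 make this contact optional. The SoA row covers only survival status and subsequent therapy, not disease status. The synopsis ends all follow-up once new anticancer therapy begins.

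In Section 9.3.2, PFS (exploratory) runs from first dose to documented progression or death from any cause. DOR (exploratory) uses the same events, counted from first response. TTP (secondary) counts progression only. For subjects with post-baseline assessments, "PFS and TTP will be censored at the last tumour assessment date"; DOR is censored in the same way. No rule there covers a death, or a progression learned by contact, that comes after a long gap without scans.

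**The concern.** Section 7.2 relies on a protocol-specified schedule, but the schedule table shows no scans between 48 weeks and 24 months after last dose. A site that follows the table stops scanning, while deaths can still be recorded for more than a year.

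Event-free subjects are then censored back at their last scan, and subjects who later die stay at risk until death. Whether a subject stays in the late risk set is decided by having a later event. The tail of the PFS and DOR curves, where durability of response to a cell therapy would be read, then reflects the follow-up rule more than the disease. Sites that follow different sections would also scan for different lengths of time, and scans not taken cannot be recovered at analysis.

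Late event-free subjects are plausible, because inclusion criterion 4 admits subjects already in long-term stable disease.

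**Working it through.** The plan gives no event count, power or precision figure for PFS, TTP or DOR, so there is no stated figure to reproduce.

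**1. Windows on the endpoint clock.** The follow-up limits run from last dose; PFS and TTP run from first dose.

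- 24 months = 24 × 52.18/12 = 104.4 weeks. The stretch without a scan column is 104.4 − 48 = 56.4 weeks. 56.4/12 = 4.7, so four full 12-weekly contacts.
- Last dose at week 2 (three weekly doses): scans end at 2 + 48 = week 50; 24 months ends at 2 + 104.4 = week 106.4.
- Last dose at week 24 (the synopsis figure for two batches): 24 + 48 = week 72 and 24 + 104.4 = week 128.4.

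**2. Mechanism.** Kaplan-Meier is S(t) = ∏(1 − d/n). If scans end at time c, every event-free subject is censored at or before c. Beyond c, n equals the number of events still to come, so the last factor is 1 − 1/1 = 0.

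Constructed example: ten subjects are event-free at a last scan at week 50, and three die at weeks 60, 72 and 84.

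- Scans stopped, seven censored at week 50: 2/3 = 0.67; × 1/2 = 0.33; × 0 = 0.
- All ten followed beyond week 84: 9/10 = 0.90; × 8/9 = 0.80; × 7/8 = 0.70.

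**3. Size under assumed inputs.** The simulation used 400,000 subjects per scenario. These assumptions are not in the documents: exponential progression with median 3, 6 or 12 months; median survival after progression 9 months; 5% per year death without progression; 8-weekly scans; none or half of the subjects with unscanned progression withdrawn for new therapy. Ranges show those last two settings.

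| Last dose | Median | Time | PFS, scans to 24 months | PFS, scans stop at 48 weeks |
|---|---|---|---|---|
| week 2 | 3 mo | week 78 | 0.020 | 0.037 |
| week 2 | 6 mo | week 78 | 0.136–0.137 | 0.150–0.156 |
| week 2 | 12 mo | week 78 | 0.355 | 0.296–0.311 |
| week 2 | 3 mo | week 105 | 0.003–0.004 | 0.001 |
| week 2 | 6 mo | week 105 | 0.057 | 0.005 |
| week 2 | 12 mo | week 105 | 0.227 | 0.010–0.011 |
| week 24 | 3 mo | week 90 | 0.008–0.009 | 0.015–0.016 |
| week 24 | 6 mo | week 90 | 0.088–0.089 | 0.108–0.110 |
| week 24 | 12 mo | week 90 | 0.284–0.286 | 0.283–0.290 |
| week 24 | 3 mo | week 127 | 0.001 | 0.000 |
| week 24 | 6 mo | week 127 | 0.036–0.037 | 0.003 |
| week 24 | 12 mo | week 127 | 0.178–0.180 | 0.007–0.008 |

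With scans stopped, the number of events after the last scan equalled the risk set in every scenario. At intermediate times the curve can be too high, because unscanned progression is missed and the death that counts instead comes later. DOR was not simulated; the mechanism carries over because its event and censoring rules are the same.

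**4. TTP** (12-month median, last dose week 2). If only scan-documented progression counts, the curve ends at week 50 at about 0.54, with no later estimate. If half of progressions are reported at the next contact and count as documented, TTP is 0.223 against 0.408 at week 78, and 0.000 against 0.274 at week 105.

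**5. Subjects concerned.** Assume 60 − 8 = 52 solid-tumour subjects. Progression-free at the last scan, last dose week 2: 52 × 0.066 = 3.4, 52 × 0.252 = 13.1 and 52 × 0.490 = 25.5 for medians of 3, 6 and 12 months. With last dose at week 24: about 1, 7 and 19.

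**The case against.** The strongest reply is that the protocol nowhere says scans stop at 48 weeks. The 48-week limit is a column heading; the scan footnote has no end date; the end-of-study visit also carries a scan, and its timing relative to week 48 is not fixed. Sections 4.1.2.3 and 7.2 can be read together, since both end at progression or new therapy and 7.2 adds a limit equal to the maximum follow-up. If sites scan on that basis, the artefact does not arise. This stands, and it makes the bias conditional. It does not remove the mismatch between Section 7.2 and the table to which it defers.

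A reader might infer several stronger things that the documents do not support:

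- **Deaths bias TTP.** They cannot, because death is not a TTP event. TTP is distorted only if contact-reported progression counts as documented, and no section says that it does.
- **Late PFS is always understated.** At weeks 78 and 90 it is slightly overstated for 3- and 6-month medians; only the end of the curve falls consistently.
- **Late deaths are certain to be collected.** Contact is mandatory only in Section 4.1.3, and under the synopsis it stops at new therapy, which removes some late deaths.

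It is also fair that Section 9.3 calls itself a summary and leaves the handling of missing data to a SAP finalised before database lock. The censoring rule can still be settled there; the scan schedule cannot.

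**Conclusion.** The point holds in conditional form. The end of tumour assessment is inconsistent across Section 7.2, the SoA and Section 4.1.2.3. If sites stop scanning 48 weeks after last dose and later deaths are counted, the censoring rule in Section 9.3.2 pulls the PFS and DOR tails towards zero whatever the true durability.

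Near the end of follow-up, with last dose at week 2, simulated PFS is 0.005 instead of 0.057 for a 6-month median and about 0.01 instead of 0.227 for a 12-month median. These sizes rest on the assumed distributions. The fall towards zero does not; it needs only that scans stop and at least one later event is counted.

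The reach is limited. Nothing before the last scan changes, including a median reached by then. PFS and DOR are exploratory, and the secondary endpoint TTP is only truncated unless contact reports count. The primary objective is safety. The change is worth making, but it does not threaten the study's main conclusion.

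**What to change.** 1. Reconcile the SoA, Section 4.1.2.3 and Section 7.2 so that tumour assessment has one end point for all subjects without progression or new therapy, including those who used up their product. State explicitly whether scans continue after 48 weeks from last dose.
2. In Section 9.3.2 or the SAP, censor PFS and DOR at the last adequate tumour assessment when death or progression is recorded after scheduled scans have ended, or after more than a fixed number of missed scan intervals (for example two).
3. State that progression reported by contact without a tumour assessment is not a TTP or PFS event.

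The cost is wording in three sections and one censoring paragraph. If the longer limit is chosen, there are also some extra standard-of-care scans for subjects still event-free after 48 weeks. The downside of the censoring rule is that a few late events are not counted and the reported curves end earlier.

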### **7.2.1      Immunological effects: Action and Follow-Up Assessment**

SUPLEXA impact on normal tissues is a theoretical concern but one which was not observed in nonclinical studies conducted in the organoid PDX or xenograft or PDX animal models. A subject experiencing an immunological event of CTCAE Grade 3 or greater will permanently discontinue study intervention.

### **7.2.2      Pregnancy**

A subject must permanently discontinue study intervention if they become pregnant but will advance to the post-treatment observational component of this study. See Appendix 4 (Section [10.4](#)) and Section [8.3.5](#) for additional details.

### **7.3           SUBJECT WITHDRAWAL FROM THE STUDY**

Subjects have the right to withdraw from the study at any time and for any reason without prejudice to their future medical care by the Investigator or at the institution.

A subject may withdraw from the study for reasons including but not limited to:

- Withdrawal by subject
- Initiation of prohibited medications (anti-cancer treatment)

- Lost to follow-up
- Study terminated by Sponsor
- Death

At the time of withdrawal from the study, if possible, an ET visit should be conducted, as shown in the SoA (Section 1.3). The subject will be permanently discontinued both from the study intervention and from the study at that time.

If the subject withdraws consent for disclosure of future information, the Sponsor may retain and continue to use any data collected before such a withdrawal of consent.

If a subject withdraws from the study, he/she/they may request destruction of any samples taken and not tested, and the Investigator must document this in the site study records.

#### 7.4 LOST TO FOLLOW UP

A subject will be considered lost to follow-up if he/she/they repeatedly fail to return for scheduled visits and are unable to be contacted by the study site.

The following actions must be taken if a subject fails to return to the clinic for a required study visit:

- The site must attempt to contact the subject and reschedule the missed visit as soon as possible and counsel the subject on the importance of maintaining the assigned visit schedule and ascertain whether or not the subject wishes to and/or should continue in the study.
- Before a subject is deemed lost to follow up, the Investigator or designee must make every effort to regain contact with the subject (where possible, 3 telephone calls and, if necessary, a certified letter to the subject's last known mailing address or local equivalent methods). These contact attempts should be documented in the subject's medical record.
- Should the subject continue to be unreachable, he/she/they will be considered to have withdrawn from the study.

## 8 STUDY ASSESSMENTS AND PROCEDURES

- Study procedures and their timing are summarized in the SoA (Section 1.3). Protocol waivers or exemptions are not allowed.
- Immediate safety concerns should be discussed with the Sponsor immediately upon occurrence or awareness to determine if the subject should continue or discontinue study intervention.
- Adherence to the study design requirements, including those specified in the SoA (Section 1.3), is essential and required for study conduct.
- All screening evaluations must be completed and reviewed to confirm that potential subjects meet all eligibility criteria. The Investigator will maintain a screening log to record details of all subjects screened and to confirm eligibility or record reasons for screening failure, as applicable.
- Procedures conducted as part of the subject's routine clinical management (e.g., blood count) and obtained before signing of the ICF may be utilized for screening or baseline purposes provided the procedures met the protocol-specified criteria and were performed within the time frame defined in the SoA (Section 1.3).
- Some visits/study procedures may be done remotely via virtual visits (telemedicine) or at home health visits. Refer to Appendix 6 (Section 10.9) and Study Reference Manual for more details

### 8.1 EFFICACY ASSESSMENTS

Planned time points for all efficacy assessments are provided in the SoA (Section 1.3).

#### 8.1.1 RECIST v1.1 (Solid Tumours Cohort only)

Objective response to treatment with SUPLEXA will be evaluated using RECIST v1.1 (Eisenhauer, 2009) as described in Appendix 5 Section 10.5. Radiographic imaging will be assessed locally by the Investigator; refer to Section 10.5.2 for methods of measurements.

#### 8.1.2 Disease Response Assessments (Haematologic Malignancies Cohort only)

Haematologic malignancies (multiple myeloma, lymphoma, and chronic lymphocytic leukemia) disease response will be assessed by the Investigator every 4 weeks ( $\pm 3$  days) per standard of care.

### 8.2 SAFETY ASSESSMENTS

Planned time points for all safety assessments are provided in the SoA (Section 1.3).

#### 8.2.1 Physical Examinations

- A complete physical examination will include, at a minimum, assessments of the cardiovascular, respiratory, gastrointestinal, and neurological systems. Height and weight will also be measured and recorded.

- A brief physical examination will include, at a minimum, assessments of the skin, lungs, cardiovascular system, and abdomen (liver and spleen).
- Investigators should pay special attention to clinical signs related to previous serious illnesses.

### **8.2.2 Vital Signs**

- Oral, aural, or surface temperature, pulse rate, respiratory rate, and blood pressure will be assessed.
- Blood pressure and pulse measurements will be assessed with a completely automated device. Manual techniques will be used only if an automated device is not available.
- Blood pressure and pulse measurements should be preceded by at least 5 minutes of rest for the subject in a quiet setting without distractions (e.g., television, cell phones).
- Vital signs will be measured in a semi-supine position after 5 minutes rest and will include temperature, systolic and diastolic blood pressure, and pulse.

### **8.2.3 Electrocardiograms**

- 12-lead ECG will be obtained as outlined in the SoA (Section 1.3) using an ECG machine that automatically calculates the heart rate and measures PR, QRS, QT, and QTc intervals.

